**Design**

Please provide a lay summary (written at 6th grade level) that includes a statement about the purpose and the general aims of the research.

This study is designed to examine if immediate weight bearing on a distal femur fracture fixed with a primary locking plate, either a distal condylar locking plate or a LISS (less invasive stabilization system), is safe and promotes more rapid fracture healing. Historically and currently patients are kept partial weight bearing after fixation of these fractures for 6-12 weeks until callous formation is observed on radiographs. Our hypothesis is that patients that are allowed to bear weight immediately will heal at least as quickly as those that have their weight bearing status protected with the added benefits from early mobilization. Fracture healing will be monitored closely by follow up appointments and complications will be documented.

Fully describe all procedures to be performed, from start to finish, numbering your procedures 1,2,3 or A, B, C (e.g., 1. Recruiting, 2. Consent, 3. Collecting data, 4. How findings will be shared, etc.).

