1. Patients will come to the Emergency Department or the POC after a supracondylar fracture or periprosthetic distal femur fracture. 2. If they fit all the inclusion and none of the exclusion criteria they will be told about the study either before their surgery if they are lucid, not in pain and can understand the study, or after their surgery when they are lucid, not in pain and can understand the study. If they are not lucid, are in pain, or cannot understand the study during this time they will not be offered participation in the study. 3. They will be told about the study with the understanding that assignment to either partial weight bearing or full weight bearing is standard of care and that physical therapy will conduct the therapy based on their group assignment 4. All questions will be answered and the subject will be given the opportunity to consent 5. They will have a metabolic bone work up done if they are 65 years of age or older which is standard of care. 6. Radiographs will be taken at 6 weeks, 3, 6 and 12 months to determine radiographic healing and/or complications with hardware which is standard of care. 7. Two independent surgeons will review radiographs to determine bridging of 3 or 4 cortices 8. We will measure time to ambulation at 2 weeks, 6 weeks and 3 months. Other variables measured include: Age, gender, date of surgery, Surgeon, Rt/Left, plate (LISS or Locking), smoking status, co-morbidities, perambulatory status, PT participation, time to discharge, discharge disposition, return to baseline ambulation, time to union, pain, Knee society score, knee flexion, radiographic evidence of healing, non-union, malunion, infection, DVT, PE, implant failure/reoperation, Vit D level, death. 9. Patients will complete a health progress report at 2 weeks, 3, 6, and 12 months post-surgery which is standard of care.

Please describe the investigational procedures that will be performed throughout the duration of the study.

Reviewing who heals faster with better outcomes based on assignment to full or partial weightbearing, both of which are standard of care, but for the study, the subject is assigned to one or the other.

Please describe the standard of care procedures that will be performed throughout the duration of the study.

Surgery and anything associated with it.

Will you be assigning or randomizing participants to groups or conditions (e.g., control, placebo)?

Yes

Describe the group assignment.

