We will be looking at two groups: those with periprosthetic distal femur fracture and those with a distal femur fracture proximal to the native knee. Both will have had their distal femur fracture repaired per standard of care. Patients in both groups will then be randomized into two groups: those allowed to bear weight immediately post operatively and those with protected weight bearing post operatively.

Does the research involve surveys/interviews/questionnaires? If so, attach a copy of the interview/survey questions on the Notes & Attachments page.

No

Describe what is known about this topic and why this study is needed. Please include at least two reference citations to support your rationale.

This study is designed to examine if immediate weight bearing on a distal femur fracture fixed with a primary locking plate, either a distal condylar locking plate or a LISS (less invasive stabilization system), is safe and promotes more rapid fracture healing. Historically and currently patients are kept partial weight bearing after fixation of these fractures for 6-12 weeks until callous formation is observed on radiographs. Our hypothesis is that patients that are allowed to bear weight immediately will heal at least as quickly as those that have their weight bearing status protected with the added benefits from early mobilization. Fracture healing will be monitored closely by follow up appointments and complications will be documented. See Lit Review under Notes and Attachments for Scientific Rationale and references.

What method are you going to use to analyze the data?

Descriptive statistics will be performed on the following variables in both groups: Age, gender, date of surgery, Surgeon, Rt/Left, plate (LISS or Locking), smoking status, co-morbidities, perambulatory status, PT participation, time to discharge, discharge disposition, return to baseline ambulation, time to union, pain, Knee society

score, knee flexion, radiographic evidence of healing, non-union, malunion, infection, DVT, PE, implant failure/reoperation, Vit D level, death.

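### The plan does not keep weight-bearing assignment from the two surgeons who judge cortical bridging, so arm-dependent reading of radiographic healing is permitted, though not shown to occur

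*Combined protocol and SAP*

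**What the plan says.** The lay summary in the Design section asks whether immediate weight bearing after locked plating "is safe and promotes more rapid fracture healing". The hypothesis is directional: "Our hypothesis is that patients that are allowed to bear weight immediately will heal at least as quickly" as those with protected weight bearing. The investigational procedure is described as "Reviewing who heals faster with better outcomes based on assignment to full or partial weightbearing".

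Healing is followed on film: "Radiographs will be taken at 6 weeks, 3, 6 and 12 months" (procedure 6). Procedure 7 gives the reading in one sentence: "Two independent surgeons will review radiographs to determine bridging of 3 or 4 cortices". The 2015 amendment entry under Protocol Notes repeats that sentence and adds nothing about who the readers are or what they may know.

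Assignment is open in care, since "physical therapy will conduct the therapy based on their group assignment" (procedure 3). Under Potential Benefits the investigators state that, if they are right, full weight bearing will bring faster healing and fewer complications. Under Confidentiality, data go onto a coded spreadsheet with the identifier file held apart, in answer to a question about privacy and confidentiality.

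For analysis, "Descriptive statistics will be performed on the following variables in both groups". The list includes radiographic evidence of healing, time to union and non-union as separate items. No primary endpoint is named.

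**The concern.** Whether a cortex is bridged is a judgement, and borderline films can be called either way. A reader who knows the arm, and who holds a view about it, may resolve those films differently in the two arms.

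The pull could go either way. The stated hypothesis favours immediate weight bearing. But the lay summary also says "Historically and currently patients are kept partial weight bearing after fixation", so a reader could equally be cautious about calling union in the arm that departs from current practice.

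A second reader does not help if both know the arm, because a shared bias does not cancel. A larger sample does not shrink it, and a descriptive comparison is shifted as much as a tested one. Patients and therapists can hardly be masked in this trial. Film readers can be, so this is the place where protection is available.

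**Working it through.** **Text check.** Three parts of the document might be thought to supply masking.

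- *The word 'independent' in procedure 7.* It may mean independent of each other or independent of the patient's care. Neither meaning keeps the assignment from the reader.
- *The coded spreadsheet under Confidentiality.* It concerns the storage of collected data. It says nothing about films or about what a reader sees.
- *The Protocol Notes entry.* It repeats procedure 7 only.

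No other section mentions masking, blinding or coded films.

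**The plan's own figure.** Subjects gives 75 in each group and 80% power. It states no endpoint, difference, alpha or sidedness, so the figure cannot be reproduced. The concern does not depend on it. I use 75 only as the size of each weight-bearing arm, which is itself an assumption about what 'group' means there.

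**Illustration of size.** The documents give no union rate and no misreading rate, so these inputs are assumed:

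- true union p at one visit, the same in both arms: 0.6, 0.7 or 0.8
- fraction m misread, in the immediate arm only: 0.10 or 0.20
- n = 75 per arm
- two-sided alpha 0.05

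Formulas:

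- Un-united read as united (favours the immediate arm): shift = (1 - p) x m
- United read as un-united (against it): shift = p x m
- Difference needed for significance: 1.96 x sqrt(2 x pbar x (1 - pbar) / 75), where pbar is the mean of the two observed proportions

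| p | m | Shift in favour (points) | Needed | Shift against (points) | Needed |
|---|---|---|---|---|---|
| 0.6 | 0.10 | 4 | 15.5 | 6 | 15.9 |
| 0.6 | 0.20 | 8 | 15.4 | 12 | 16.0 |
| 0.7 | 0.10 | 3 | 14.5 | 7 | 15.1 |
| 0.7 | 0.20 | 6 | 14.2 | 14 | 15.5 |
| 0.8 | 0.10 | 2 | 12.6 | 8 | 13.7 |
| 0.8 | 0.20 | 4 | 12.3 | 16 | 14.4 |

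Worked case, last row, against: the immediate arm is read as 0.8 x (1 - 0.20) = 0.64, so pbar = (0.80 + 0.64)/2 = 0.72. The difference needed is 1.96 x sqrt(2 x 0.72 x 0.28 / 75) = 1.96 x 0.0733 = 0.144, or 14.4 points. The shift is 16 points, which is 12 of 75 patients. The standard error of the observed difference is sqrt((0.80 x 0.20 + 0.64 x 0.36)/75) = 0.0722. The chance of a significant result with no true difference is therefore about Phi((0.160 - 0.1437)/0.0722) = Phi(0.226), or about 59%.

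In the other eleven cells the expected shift is below the difference needed. That does not make them harmless. For p = 0.6 and m = 0.20 in favour (8 points), the same calculation gives a rejection rate of about 17% against a nominal 5%.

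**Choice of benchmark.** The difference detectable with 80% power at 75 per arm is 15.0 to 22.7 points over this range of p, and in every cell the shift is below the detectable difference for the same p and direction. That comparison gives no reassurance, because a bias need only approach the smaller significance threshold to produce false findings.

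**Workload.** 150 patients x 4 film visits = 600 patient-visits, and 600 x 2 readers = 1,200 readings.

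**The case against.** The strongest reply is that the evidence is silence. The document is an ethics-board questionnaire, and none of its questions asks about masking of assessors. The readers are called independent. If that means independent of the patient's care, part of the risk is already met. The link to a result is also conditional: no primary endpoint is named, only descriptive statistics are planned, and the definition of bridging and the handling of reader disagreement are not settled either.

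Much of this stands, and it limits what may be claimed. A reader might infer that the films are or will be read unmasked, but the text does not establish that. A reader might infer that time to union and non-union are biased too. They are listed separately, and the plan does not say that they come from this reading. A reader might take the stated hypothesis to mean that any bias favours immediate weight bearing, but the description of current practice supports the opposite pull as well.

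What does not stand is that the gap is only a missing detail. Procedure 7 could be followed to the letter by two surgeons who know every patient's arm. Nor does descriptive analysis protect the comparison.

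**Conclusion.** The concern holds in a limited form. As written, the plan permits arm-dependent judgement of bridging, the only radiographic healing assessment it describes, in a study that asks which arm heals faster. It does not show that this happens.

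The size and direction of any bias are unknown. The shifts of 2 to 8 points in favour and 6 to 16 points against rest wholly on the assumed union rates, misreading rates, one-arm error and 75 per arm. They show what is possible, not what is likely. Because the plan states no alpha and no test, the rejection rates above are not error rates of this trial.

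The change should be made, but it is not a fatal flaw. Confidence is medium, because the literature review and consent form were not available, and a masking procedure may be in use without being written down.

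**What to change.** Amend procedure 7 so that the two planned surgeons make the research reading of bridging separately from each other, on de-identified films coded by a coordinator, without access to assignment, therapy notes or the clinical reading. Routine clinical reading stays as it is. If masked reading is already the practice, one sentence saying so is enough.

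The 2019 entries in Protocol Notes show a study some years old, but not that any film has been read. If films have been read without masking, re-read them masked or flag them in the report.

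Cost: coordinator time to code up to 600 patient-visits. Consent Procedures shows coordinators on the team, and Confidentiality describes a separate identifier file. Surgeon time rises, to at most 1,200 readings, if the research reading is not already separate from the clinical one; any re-reading adds to this. No extra reader or film is needed. Funding Source records no secured funding, and the documents give no unit costs.

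Masking will be incomplete where a reader recognises a case, and it does nothing for the other outcomes assessed with the arm known.

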### Expedited Review

Is this study only minimal risk?

Yes

Does the research qualify for Expedited Review Category 1 - clinical studies of FDA-approved drugs or medical devices? (See More Information)

No

Does the research qualify for Expedited Review Category 2 - blood sample collection? (See More Information)

No

Does the research qualify for Expedited Review Category 3 - noninvasive collection of biological specimens? (See More Information)

No

Does the research qualify for Expedited Review Category 4 - noninvasive standard of care procedures? (See More Information)

No

Does the research qualify for Expedited Review Category 5 - evaluation of data (e.g., medical records review)? (See More Information)

Yes

Does the research qualify for Expedited Review Category 6 - voice, video, digital, or image recordings? (See More Information)

No

Does the research qualify for Expedited Review Category 7 - behavior, surveys, interviews, etc.? (See More Information)

No

Briefly describe how the research meets the requirements of the expedited category(ies) selected.

Full or partial weight bearing after a supracondylar distal femur fracture is standard of care. Review of medical records to determine the variables we want to collect: standard of care patient reported outcomes at regular follow up visits.

Does the study involve intervention and/or manipulation of the subjects or the subjects' environment (e.g., educational intervention or training, experimental or quasi-experimental design)?

No

Is the research categorized as interventional medical research?

No

Will subjects intentionally be deceived as to the purpose of the study?

No

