### Subjects

Indicate the maximum number of subjects to be enrolled or medical records to be reviewed at all sites by the WVU or VAMC research team.

150

Provide a rationale for choosing your sample size.

75 in each group provides 80% power to detect a difference between the groups.

State the requirement(s) to become a participant in the study (e.g., age range, sex, language spoken, class enrollment/ranking).

All patients aged > 18 yo with a distal supracondylar femur fracture will be included, both male and female; Supracondylar distal femur fractures treated with a locked plate, either a distal condylar locking plate or a LISS (less invasive stabilization system), including peri-prosthetic fractures. CPT code 27511

Explain why selection of participants will be equitable addressing gender, ethnicity, and/or race of subjects.

Patients with an intracondylar split, polytrauma patients with associated trauma that will inhibit their ability to weight bear, metastatic disease, incomplete follow up, those with questionable ability to bear weight (ie advanced dementia), open fractures with bone loss, will not be included. Those who are in pain, not lucid, or unable to understand the study at time of consent will not be included.

In outline format and chronological order, describe what will be done to identify and recruit participants (e.g., A, B, C or 1, 2, 3).

1. Patients will come to the Emergency Department or the POC after a supracondylar fracture or periprosthetic distal femur fracture. 2. If they fit all the inclusion and none of the exclusion criteria they will be told about the study either before their surgery if they are lucid, not in pain and can understand the study, or after their surgery when they are lucid, not in pain and can understand the study. If they are not lucid, are in pain, or cannot understand the study during this time they will not be offered participation in the study.

Will any of the subjects be less than 18 years old?

No

Will your study target populations such as pregnant women, fetuses, neonates, or any groups likely to be vulnerable to coercion or undue influence such as children, prisoners, individuals with impaired decision-making capability or economically or educationally disadvantaged persons?

No

Does this research involve participants who could be coerced or unduly influenced, such as current students/employees of research team members?

No

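### Not including patients with incomplete follow-up, read as written, removes randomised patients from every comparison by arm; return to baseline ambulation also has no assessment time

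*Combined protocol and SAP*

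**What the plan says.** There is one document, the combined protocol and SAP.

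- **Exclusions (Subjects).** The list of patients who will not be included contains "metastatic disease, incomplete follow up, those with questionable ability to bear weight". It does not say when follow-up is judged incomplete. No rule for missing data appears elsewhere.
- **Aim (Design).** The hypothesis is that patients bearing weight immediately "will heal at least as quickly as those that have their weight bearing status protected with the added benefits from early mobilization". The investigational procedure is described as "Reviewing who heals faster with better outcomes based on assignment to full or partial weightbearing".
- **Ambulation (Design, procedures, item 8).** "We will measure time to ambulation at 2 weeks, 6 weeks and 3 months". Return to baseline ambulation follows in the list of other variables, with no visit, window or definition.
- **Analysis (Design, analysis method).** Descriptive statistics are planned for a list that includes "PT participation, time to discharge, discharge disposition, return to baseline ambulation, time to union". Time to ambulation is not on that list.
- **Contacts (Design, procedures, items 6 and 9).** "Radiographs will be taken at 6 weeks, 3, 6 and 12 months", for healing and hardware. "Patients will complete a health progress report at 2 weeks, 3, 6, and 12 months post-surgery"; the content of this report is not described.
- **Data source (Expedited Review).** "Review of medical records to determine the variables we want to collect: standard of care patient reported outcomes at regular follow up visits".

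**The concern.** Whether follow-up was complete is normally learned after a patient has been randomised. If that decides who is analysed, the arms compared are no longer the arms that randomisation created. Patients may stop attending because they recover badly, die, move to another facility or feel well, and these reasons may be more common under one weight-bearing regimen than the other. A difference between arms can then appear where none exists, or a real one can be hidden. This affects union, complications and implant failure as much as walking.

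The second issue is narrower. Return to baseline ambulation is a listed outcome without a time. If it is taken from the chart at whichever visit recorded it, one patient may be read at 6 weeks and another at 12 months, and the two arms' percentages need not describe the same stage of recovery. Meanwhile time to ambulation has a schedule but no place in the analysis list.

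**Working it through.** **The plan's own figure.** The only sample-size statement is 75 per group for 80% power. It gives no endpoint, significance level or effect size, so it cannot be reproduced. This point neither needs it nor disputes it.

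**Step 1: can the exclusion act after randomisation?** Item 2 of the Design procedures applies the exclusion criteria before a patient is told about the study, which allows a screening meaning. But the words describe a state of follow-up, and no timing is attached. In the same answer, the condition about pain, lucidity and understanding is tied to the time of consent. As written, the rule can be applied afterwards.

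**Step 2: how large could the distortion be?** None of these inputs is in the documents; all are assumed:
- p = true share back to baseline, the same in both arms: 50-70%
- m = share of each arm dropped: 10-20%
- r = share back to baseline among those dropped from one arm. The other arm loses patients at random, so its observed share stays at p.

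False difference = (p - r·m)/(1 - m) - p

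| p | m | r | Observed share, selective arm | False difference |
|---|---|---|---|---|
| 0.5 | 0.1 | p/2 | 0.475/0.9 = 52.8% | 2.8 points |
| 0.6 | 0.2 | p/2 | 0.54/0.8 = 67.5% | 7.5 points |
| 0.7 | 0.2 | p/2 | 0.63/0.8 = 78.75% | 8.8 points |
| 0.5 | 0.1 | 0 | 0.5/0.9 = 55.6% | 5.6 points |
| 0.6 | 0.2 | 0 | 0.6/0.8 = 75% | 15.0 points |
| 0.7 | 0.2 | 0 | 0.7/0.8 = 87.5% | 17.5 points |

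If m and r are the same in both arms, both observed shares move together and the false difference is 0.

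**Step 3: what does keeping the patients achieve?** Take p = 0.6, m = 0.2, r = 0 and 75 per arm. The selective arm has 45 observed returns and 15 unknown. The random-loss arm has 36 observed returns and 15 unknown.
- Observed patients only: 45/60 v 36/60 = 75% v 60%, a difference of 15 points.
- Unknown counted as not returned in both arms: 45/75 v 36/75 = 60% v 48%, a difference of 12 points.
- Opposite extremes: 45/75 v 51/75 = 60% v 68%, a difference of -8 points; and 60/75 v 36/75 = 80% v 48%, a difference of +32 points.

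So retaining patients does not by itself remove the bias when the late status is unknown. Counting unknown as not returned is a check and not a correction. The two extremes bracket the true value of 0 and show how little the data then settle.

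**Step 4: precision of a late comparison.** The 95% half-width is 1.96 × √(2p(1 - p)/n). With n = 75 per arm it is 16.0, 15.7 and 14.7 points for p = 0.5, 0.6 and 0.7. With n = 60 it is 17.9, 17.5 and 16.4. The 75 assumes that the maximum of 150 is enrolled and split equally by weight-bearing arm.

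**Step 5: dates for ambulation.** The three dated assessments end at 3 months. The plan's contacts, taken together, fall at 2 weeks, 6 weeks, 3, 6 and 12 months. No date is attached to return to baseline, so a common set of times can be fixed without a new visit.

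**The case against.** - **The phrase may mean patients not expected to attend follow-up, judged at screening.** This stands as a possible reading. The text does not say so, and if it is meant the wording still has to change.
- **The 2.8 to 17.5 points rest on one-sided loss.** This stands. Random loss in one arm and selective loss in the other is an unfavourable pattern, and equal patterns give zero. The range shows what the rule permits; it does not predict this trial's bias. Nor does it measure the effect of leaving return to baseline undated, for which no figure can be given.
- **Keeping the patients does not supply their missing outcomes.** This stands, as step 3 shows. The gain is partial follow-up, such as a patient seen at 6 but not 12 months, and a visible account of who was lost.
- **The mobility claim concerns early benefit.** This stands. The three early assessments suit it, and late mobility is not a stated aim. A reader might infer that the schedule fails the hypothesis; the documents do not support that.
- **Late mobility may already be recorded.** A reader might infer that no mobility data after 3 months will exist. The documents do not support that either: the 6- and 12-month health progress report or the charts may hold some. Its content is not shown, so this cannot be judged either way.

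**Conclusion.** The concern holds in two parts of unequal weight.

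The main part is the exclusion for incomplete follow-up. Applied as written, it removes randomised patients on an event after randomisation and can bias every comparison by weight-bearing arm. The illustrative size is 2.8 to 17.5 points on return to baseline, resting wholly on the assumed return rates, the assumed share dropped and loss that is selective in one arm only. It would be too strong to say that the trial will be biased by this amount, or that the sponsor certainly intends to drop patients after randomisation.

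The secondary part is a gap in detail: return to baseline ambulation is undated, and time to ambulation is missing from the analysis list. That leaves comparability of these outcomes between arms unsecured. It does not undermine the healing or safety aims. At about ±15 to 18 points, a late comparison could neither establish nor rule out a modest lasting benefit.

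**What to change.** **Subjects.** Delete incomplete follow-up from the exclusions. If expected inability to attend is meant, state it as a criterion judged before randomisation.

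**Design, analysis method.**
- Keep every randomised patient in the assigned weight-bearing arm with the data available; for example, censor time to union at the last visit.
- Show deaths and missing data by arm at each time point.
- Accompany the percentages with a simple sensitivity analysis: missing counted as not returned, and preferably also the two opposite extremes of step 3.
- Add time to ambulation to the variable list.
- Report it and return to baseline by randomised weight-bearing arm, with 95% confidence intervals, as descriptive results. Naming the arm matters because the section uses the word groups for both fracture type and weight-bearing assignment.

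**Design, procedures, item 8.** Keep the three early assessments. Record return to baseline (yes/no) in both arms at 2 weeks, 6 weeks, 3, 6 and 12 months. Judge it against pre-injury status if that is what perambulatory status means; the study team should confirm this. State whether the health progress report already captures it.

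**Cost.** There is no new visit or test. One yes/no field at 5 contacts for 150 patients is at most 5 × 150 = 750 entries, some perhaps already charted. Clinicians must record the status consistently, since the plan relies on record review. A protocol amendment is needed. The Protocol Notes show a 2015 amendment and a 2019 renewal, so any patient already past a visit could not be assessed prospectively for it. Some late data will still be missing and must be reported.

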### **Consent Procedures**

Will SIGNED informed consent be obtained from subjects (paper-based and/or electronic)?

Yes

Will the informed consent form be translated into any other language(s)?

No

Is a waiver of informed consent being requested (i.e., there will be no consent process at all)?

No

Is a waiver of the requirement to obtain written documentation of the consent process being requested (if yes, attach the information to be provided to the participants)?

No

Are you requesting an alteration of consent (e.g., short form, braille consent or witnessed verbal consent)?

No

For remote or in-person electronic consent, complete an e-IC worksheet from the [OHRP Forms page](#) and attach it to the submission.

If only paper-based in-person consent will be used, describe the consent process. Address the following separately:

1. When will prospective participants be approached for consent?
2. Where will the consent occur?
3. How will the research and the consent materials be explained, and how and when will questions be answered?

. Patients will come to the Emergency Department or the POC after a supracondylar fracture or periprosthetic distal femur fracture. 2. If they fit all the inclusion and none of the exclusion criteria they will be told about the study either before their surgery if they are lucid, not in pain and can understand the study, or after their surgery when they are lucid, not in pain and can understand the study. If they are not lucid, are in pain, or cannot understand the study during this time they will not be offered participation in the study. 3. They will be told about the study with the understanding that assignment to either partial weight bearing or full weight bearing is standard of care and that physical therapy will conduct the therapy based on their group assignment 4. All questions will be answered and the subject will be given the opportunity to consent.

Indicate who will be consenting subjects and describe the process of training all personnel who will be obtaining consent.  
Research coordinators may consent subjects. They have been trained and have been conducting the consent process for years.

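### The plan calls both weight-bearing regimens standard of care and answers that the study involves no intervention, against its own rationale and randomisation; no review of harm by arm is described before the end

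*Combined protocol and SAP*

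**What the plan says.** **Current practice.** The lay summary in the Design section states "Historically and currently patients are kept partial weight bearing after fixation of these fractures for 6-12 weeks", and adds that the study examines whether immediate weight bearing is safe and speeds healing. The background answer later in that section repeats both statements.

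**Standard of care.** Under investigational procedures, the Design section says of the two regimens "both of which are standard of care", and adds that the study decides which of them a subject receives. The Expedited Review section says "Full or partial weight bearing after a supracondylar distal femur fracture is standard of care". The Consent Procedures section has patients told that "assignment to either partial weight bearing or full weight bearing is standard of care".

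**Type of study.** The Design section answers Yes to "Will you be assigning or randomizing participants to groups or conditions" and describes randomisation to immediate or protected weight bearing. The Expedited Review section answers No to a question about intervention or manipulation of subjects, whose own examples include experimental design. It also answers No to "Is the research categorized as interventional medical research". It answers Yes to minimal risk and selects one expedited category only, number 5 (evaluation of data, such as records review).

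**Harm.** The lay summary says that "complications will be documented". Non-union, malunion, infection, DVT, PE, implant failure or reoperation, and death are on the variable list. The analysis answer promises descriptive statistics on that list in both groups.

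**The concern.** Two pairs of statements do not fit together. One pair concerns what patients ordinarily receive after this surgery; the other concerns whether the study intervenes at all. The standard-of-care statement matters because it is the reason given for the expedited category and is part of the planned explanation to patients. If it is inaccurate or incomplete, the board has judged the review route, and patients will judge participation, on a description that the rationale does not share.

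The treatment of harm adds to this. Safety is a stated question and the relevant events are collected, but no point before the final tables is described at which anyone compares the arms. If groups means randomised arms in the sample-size statement, up to 75 patients are assigned to the regimen that the rationale contrasts with current practice.

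**Working it through.** The main finding is a comparison of texts. The only design figure in the documents, 75 per group for 80% power (Subjects section), has no bearing on it. That figure cannot be reproduced in any case, because no endpoint, effect size, variability or event rate, or significance level is given.

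**Step 1: current practice**

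| Place | Statement |
|---|---|
| Design, lay summary and background | Partial weight bearing for 6-12 weeks is past and current practice; safety of immediate weight bearing is in question |
| Design, investigational procedures | Both regimens are standard of care |
| Expedited Review, justification of category | Either regimen is standard of care |
| Design, procedures list; Consent Procedures | Patients are told that assignment to either is standard of care |

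If both regimens are in ordinary use, the first row misdescribes practice. If they are not, the other three rows do. No sentence in the documents connects the two accounts.

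**Step 2: type of study**

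The Design section randomises, and says that the study determines which regimen a subject receives. The intervention question in the Expedited Review section names experimental design among its examples and is answered No. This conflict remains even if both regimens are accepted practice, because randomisation sets the weight-bearing status. The Potential Benefits section expects the full weight-bearing subjects to heal faster with fewer complications, so the assigned regimen is what is being tested.

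**Step 3: harm**

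The group-assignment answer uses the word groups first for the two fracture types (periprosthetic and native knee) and then for the two randomised arms. The analysis answer then refers to both groups without saying which. A final summary by arm is the likely meaning, but it is not stated. No monitoring body, interim look by arm or between-arm comparison of harm appears.

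**Step 4: what a table by arm could show (illustration)**

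The documents give no harm rates, so the rates below are assumptions. Half of 150 is 75, or about 37 per arm. Let X and Y be independent binomial counts with n = 37 and rates p1 and p2. The probability of an excess of at least four events is P(Y - X >= 4), the sum of P(X = i) P(Y = j) over all j >= i + 4.

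| p1 v p2 | Expected events (37 × p1 v 37 × p2) | P(excess >= 4) |
|---|---|---|
| 5% v 10% | 1.85 v 3.7 | 23% |
| 10% v 20% | 3.7 v 7.4 | 52% |
| 5% v 20% | 1.85 v 7.4 | 77% |
| 5% v 5% | 1.85 v 1.85 | 3% |
| 10% v 10% | 3.7 v 3.7 | 8.5% |

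All rows suppose complete outcomes for 37 per arm. Follow-up runs to 12 months, so fewer may be complete at half enrolment. With 25 or 18 per arm complete (assumed), the 77% falls to 54% or 33%.

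**The case against.** **The two accounts of practice may be compatible.** Standard of care can mean within accepted practice, while the rationale describes what is customary. A trial may compare two accepted regimens and still ask about safety. This stands in part: a false statement to participants is not shown. But the documents never draw that distinction, and it leaves the intervention answer in conflict with the randomisation.

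**A reader might infer that harm is not reviewed by arm at all.** The documents do not support that. The listed harms are to be summarised descriptively in both groups at the end. What is absent is an explicit definition of the groups and any look by arm before the end.

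**A reader might infer that the classification caused the missing look, or that the minimal-risk answer rests on the standard-of-care statement.** Neither link is written down. That statement is given as the reason for the expedited category only; the minimal-risk answer carries no reason.

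**Some material is unseen.** The consent form and the attached literature review are not available here. The planned explanation does tell patients that therapy follows their group assignment, and the form may say more. The Protocol Notes show that renewals are filed but not what they report on harm.

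**A reader might infer that a mid-trial table would keep some 37 further patients out of a worse arm.** It would not by itself: a table without a trigger stops no enrolment, and renewals are not tied to half enrolment. The illustration also shows that a table reveals large excesses far better than small ones.

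**Conclusion.** The point holds as an inconsistency that should be corrected. The rationale and the standard-of-care statements give different accounts of usual practice, and the randomisation contradicts the No to intervention or manipulation. The No to interventional medical research needs correction or a reason; the board's definition of that term is not in the documents, so the right answer cannot be settled from them. The consequences that can be demonstrated are that the expedited category and the planned consent explanation use the disputed statement.

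On harm, the supportable conclusion is narrower: a final descriptive summary is planned, probably but not explicitly by arm, and no earlier review by arm is described. The value of adding one depends on rates that the documents do not give and on how many outcomes are complete at each renewal. The main conclusion depends on none of these assumptions.

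**What to change.** 1. Reconcile the lay summary and background in the Design section with the statements on standard of care in the Design, Expedited Review and Consent Procedures sections. Check that the consent explanation says that randomisation sets weight-bearing status, and how each arm relates to the usual practice described.
2. In the Expedited Review section, correct the intervention/manipulation answer to match the randomisation. Correct or justify the answer on interventional medical research. Ask the review board to reconsider the expedited category and the minimal-risk answer.
3. State that groups in the analysis means the randomised arms. Unless renewals already do so, include in each a descriptive table by assigned arm of implant failure or reoperation, non-union, infection, DVT, PE and death. Send it to the review board and not to the surgeons who read the radiographs.

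The cost is one amendment, possible re-review by the board, and one table per renewal. No test or boundary is proposed, so no type I error is spent. The remaining risk is that a table reaching the study team could influence outcomes that involve judgement, such as union and reoperation; hence the choice of recipient. No clinical rule is proposed.
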